Research Proposal

Use of a “flash-free” adhesive resin for orthodontic bracket bonding: a clinical study of bonding time, bond survival, and adhesive remnant cleanup

[name], Dr med dent, PhD, [name], MS

Division of Orthodontics, Department of Developmental and Surgical Sciences, University of Minnesota

Background:

The time required for bracket bonding and cleanup of remnant adhesive from the enamel surface after bracket debonding are important determinants of the duration of the two longest appointments during orthodontic treatment. The development of “flash-free” adhesives resin for orthodontic bracket bonding, which is due on the market in the near future, now promises a decrease in chair time for both patient and orthodontist. However, questions remain regarding the bonding time and bond survival of orthodontic brackets bonded using these adhesives, and the time required for adhesive remnant cleanup. These factors will be critical in determining the acceptance of these new “flash-free” adhesive resins in the orthodontic community.

Purpose:

The purpose of this study is to compare (1) bonding time, (2) bond survival, (3) amount of adhesive remaining on the tooth surface after bracket debonding, and (4) time required for adhesive remnant cleanup between a new “flash-free” and a conventional adhesive resin for orthodontic bracket bonding.

Methods:

Thirty consecutive patients presenting for comprehensive orthodontic treatment with fixed appliances at the University of Minnesota, who are willing to participate, will be included in the initial study. Selection criteria will include full permanent dentition through the first molars, teeth with sound, non-carious buccal enamel and no pretreatment with chemical agents such as hydrogen peroxide, and no previous orthodontic treatment with fixed appliances. The patients will have their maxillary incisors, canines, and premolars bonded with ceramic orthodontic brackets pre-coated with a “flash-free” adhesive resin (Clarity Advanced Brackets “flash-free”, 3M Unitek Monrovia, CA, USA) on one side and a conventional adhesive resin (Clarity Advanced Brackets APC II, 3M Unitek) on the other side. The side allocation and order of bonding will be randomized for each patient.

A total of ten calibrated clinicians will perform the clinical procedures together with their dental assistants.

Bonding time

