The patient's teeth will be polished using a fluoride-free prophylaxis paste (Topex Prep&Polish, Sultan Healthcare, Hackensack, NJ, USA) on a rubber cup attached to a low speed handpiece, etched with 35% phosphoric acid (Temrex, Freeport, NY, USA) for 30 seconds, rinsed with water, air-dried, and primed using a conventional primer (Transbond Light Cure Adhesive Primer, 3M Unitek) following the manufacturer's instructions. The teeth will then be bonded according to the predetermined protocol with the "flash-free" product on one side (group 1) and the conventional (APC II) product on the other side (group 2) using a direct bonding technique. Excessive adhesive in group 2 will be removed with a sharp scaler. The adhesive will be light cured for 20 seconds (5 seconds on each side of the bracket) with a light-emitting diode polymerization device (Ortholux LED, 3M Unitek). The distance between the exit window and the adhesive surface will be maintained at less than 5 mm in order to obtain adequate polymerization. The time taken to bond each side will be timed to the nearest second using a digital stopwatch.

Bond survival

Possible bond failure will be recorded at standardized intervals of four weeks. In case of a bond failure, the patients will be asked about a possible explanation for the bond failure. Bond failure as a consequence of habits and trauma will be excluded from the evaluation.

Adhesive remnant cleanup

After completion of orthodontic treatment, the brackets will be debonded following the manufacturer's instructions. The order of debonding will be randomized for each patient. Once the brackets are debonded, the adhesive remnant index (ARI; Årtun and Bergland, 1984) will be scored under $\times 10$ magnification using an optical microscope (MVX10, Olympus, Tokyo, Japan).

Remaining adhesive will be removed from the tooth surfaces using a tungsten carbide finishing bur (H 283-21-012, Brasseler, Savannah, GA, USA) in a low speed handpiece until the enamel has regained its natural gloss (David *et al.*, 2002). Satisfactory removal of the remnant adhesive will be verified by visual inspection under a dental operating light. The time taken to clean up the residual adhesive in each quadrant will be timed to the nearest second using a digital stopwatch.

Statistical analysis

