Descriptive statistics will be applied to the data to obtain mean values and standard deviations, and the data will be tested for normality (Kolmogorov-Smirnov test). Differences between the groups will be tested for statistical significance using a Student's *t*-test if the data are normally distributed and a Mann-Whitney U test if the data are non-normally distributed. Bracket survival times will be compared using a Cox's *F* test. A Cochran-Armitage test will be used to determine if there is an association between group membership and ARI. For all tests, *P*-values of less than 0.05 will be considered statistically significant.

Approval:

Approval to conduct this study will be obtained from the Institutional Review Board at the University of Minnesota. Informed consent will be obtained from all participating patients. In case of minors, consent will be obtained from a parent or guardian; assent will be obtained from the minor.

Anticipated outcomes:

Following completion of this study it is expected that significant information will be gained regarding the following:

1. The time required for direct bracket bonding with a “flash-free” orthodontic adhesive resin compared to a conventional adhesive resin together with a possible decrease in chair time when using a “flash-free” product.
2. Bond survival of brackets bonded with a “flash-free” orthodontic adhesive resin compared to a conventional adhesive resin.
3. The amount of adhesive remaining on the tooth surface after bracket debonding using the above products.
4. The time required for adhesive remnant cleanup using the above products and possible decrease in chair time when using a “flash-free” product.
5. An independent assessment of the clinical performance, suitable for peer-reviewed publication, of a new “flash-free” orthodontic adhesive resin.

References:

Årtun J, Bergland S (1984). Clinical trials with crystal growth conditioning as an alternative to acid-etch enamel pretreatment. *Am J Orthod* 85:333–340.

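### The order of debonding is randomised, but the plan gives no order for the timed cleanup that follows, and does not have that order recorded or analysed

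*Combined protocol and SAP*

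**What the plan says.** The end-of-treatment visit is described under Methods, Adhesive remnant cleanup, in this sequence:

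- Debonding: "The order of debonding will be randomized for each patient".
- ARI scoring under magnification: "Once the brackets are debonded, the adhesive remnant index" is scored.
- Cleanup: "Remaining adhesive will be removed from the tooth surfaces using a tungsten carbide finishing bur", with the end point judged by eye: "Satisfactory removal of the remnant adhesive will be verified by visual inspection under a dental operating light".
- Timing: "The time taken to clean up the residual adhesive in each quadrant will be timed to the nearest second using a digital stopwatch".

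For the other timed outcome, the opening part of Methods says "The side allocation and order of bonding will be randomized for each patient". On personnel it says "A total of ten calibrated clinicians will perform the clinical procedures together with their dental assistants".

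Under Statistical analysis, "Differences between the groups will be tested for statistical significance using a Student's *t*-test", or a Mann-Whitney U test if the data are not normal. The text mentions no pairing and no term for order.

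The documents do not state which quadrant is cleaned first, whether cleanup follows the debonding order, whether the order is written down, or whether anyone is masked.

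**The concern.** Cleanup time is one of the four stated purposes. One operator working through two quadrants in succession may be quicker or slower on the second because of practice, fatigue or bur wear. If one product tends to be cleaned first, that first/second effect is added to the product effect. The plan guards against this at bonding by randomising the order of the step that is timed. At the final visit the randomised order is attached, as written, to a step that has no time outcome.

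If the order is not recorded, nobody could later tell whether the split was even, or adjust for it. The end point of cleanup is also a visual judgement, which leaves more room for first/second differences than a fixed mechanical end point would.

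**Working it through.** **No figure to reproduce.** The plan gives 30 patients and a 0.05 significance level. It gives no standard deviation, effect size, power or order effect. The order shift k, the share p and the within-patient correlation below are therefore assumptions. Tests are taken as two-sided.

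**Set-up.** Take the within-patient difference in cleanup time (flash-free minus conventional), with SD 1 when there is no order effect. Suppose it moves by +k if flash-free is cleaned first and by −k if second. Let p be the share of patients in whom flash-free goes first. Then:

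- Bias = k(2p − 1).
- SD of the observed difference = √(1 + 4p(1 − p)k²).
- Standardised bias = bias × √30 / SD.

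**When side allocation is enough.** If every operator starts on the same anatomical side, random side allocation makes p = 0.5 in expectation and the bias is 0 for any k. The same holds if cleanup order is randomised.

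**When it is not.** With k = 0.5 and p = 0.7, bias = 0.5 × 0.4 = 0.20 SD. The SD is √(1 + 0.84 × 0.25) = 1.10, and the standardised bias is 0.20 × 5.477 / 1.10 = 0.996. The normal approximation then gives a type I error of about 17%; simulation with the t-test gives 16%. With p = 0.8, bias = 0.30 SD, SD = √(1 + 0.64 × 0.25) = 1.077, and standardised bias = 1.526. The approximation gives 33% and simulation 31–32%.

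Simulated type I error, paired t-test, 30 patients, no true product difference:

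| Order shift k (SD of difference) | Bias at 70:30 | Type I error at 70:30 | Bias at 80:20 | Type I error at 80:20 |
|---|---|---|---|---|
| 0.1 | 0.04 | 5–6% | 0.06 | 6% |
| 0.25 | 0.10 | 8% | 0.15 | 12% |
| 0.5 | 0.20 | 16% | 0.30 | 31–32% |

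**Under the test as planned.** For a two-sample t-test with k = 0.5 and within-patient correlation 0.3 to 0.7, type I error is 1–11% at 70:30 and 4–23% at 80:20. It is lower because a test that ignores positive pairing is conservative. The bias in the estimated difference is the same.

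**With order recorded and fitted.** In a paired analysis with an order term, type I error returns to about 5% at both 70:30 and 80:20. If one product is always cleaned first, order and product are fully confounded and no term can be fitted.

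**Precision when order is randomised.** Take a true difference of 0.53 SD, which 30 pairs detect with about 80% power when there is no order effect. Power without and with the order term is about 78% and 78–79% at k = 0.25, and 71% and 78–79% at k = 0.5. Nothing is biased in either case.

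**A limit of these figures.** They let the starting side depend on product. If it depends on visible remnant, p departs from 0.5 only where remnant differs by product. The result is then mainly a distorted size of the cleanup-time difference rather than a false positive from nothing. Adjusting afterwards is also less secure there, because remnant influences both the order and the time. Randomising the order is therefore better than recording it alone.

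**The case against.** The strongest defence is that the sentence on debonding order sits in a section whose only stopwatch outcome is cleanup time, so the authors may well have meant the order to run through the whole visit. That is plausible. It makes the defect an ambiguity, but one that decides how the visit is run, since ARI scoring separates the two steps and nothing links their orders.

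The second defence is that side is already randomised. Bias then needs operators to choose the starting side by product or remnant, in a consistent direction across ten clinicians, and also needs a material first/second effect. The documents show none of these. This stands, and it is why the figures are illustrations only. At a shift of 0.1 SD the consequence is negligible.

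A reader might infer more than the text supports:

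- That the plan leaves cleanup order to an unmasked operator. It is silent on both the order and the masking.
- That the person cleaning has just seen the ARI scores. The documents do not say who scores the ARI or who sees the result.
- That randomising the debonding order serves no purpose. It may protect the ARI comparison, which is itself a stated purpose.
- That the bonding-time comparison is biased for want of an order term. Order is randomised there, so the omission costs precision only.

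Finally, an order term presupposes a within-patient analysis, which the plan does not name. Pairing is a separate and larger matter for efficiency, and this part of the remedy depends on it.

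**Conclusion.** The point holds as a gap in the conduct of the cleanup step: the timed procedure has no stated or recorded order, although the plan controls order for the timed bonding step. It does not establish that the cleanup comparison will be biased. Bias arises only if the starting side is related to product, directly or through visible remnant, and if going first or second matters.

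Under those assumptions the effect on a paired test runs from negligible (5–6% type I error at a shift of 0.1 SD) to serious (about 31% at 0.5 SD and an 80:20 split). The inflation is smaller under the unpaired test as planned. The missing order term for bonding time is a minor, optional improvement. The case for acting is that prevention is almost free, whereas an order that was never recorded cannot be recovered.

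**What to change.** 1. Under Adhesive remnant cleanup, state that cleanup of the two quadrants follows the same randomised order as debonding in that patient.
2. Record the order actually used, including departures from the assigned order.
3. Under Statistical analysis, specify a within-patient (paired) comparison of cleanup time with order (first or second) as a term. Use the same term for bonding time, described as a gain in precision only.
4. State whether the operator, the timekeeper or the ARI scorer is masked to product and, if not, say so.

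The cost is a clause in the protocol, one recorded field and one degree of freedom. No additional procedure, visit or staff is needed.

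### No masking is specified for cleanup time or the adhesive remnant index, although cleanup stops on a visual judgement; withholding the side allocation at debonding is a cheap partial safeguard

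*Combined protocol and SAP*

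**What the plan says.** The relevant text is in Methods, mainly under Adhesive remnant cleanup.

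- **Stopping rule.** Remaining adhesive is removed with a bur "until the enamel has regained its natural gloss".
- **Check on completion.** "Satisfactory removal of the remnant adhesive will be verified by visual inspection under a dental operating light". The person who verifies is not named.
- **Timing.** "The time taken to clean up the residual adhesive in each quadrant will be timed to the nearest second using a digital stopwatch". The timekeeper is not named.
- **ARI.** The index is scored at tenfold magnification, after the brackets come off and before cleanup. No scorer and no agreement check are given.
- **Brackets.** One side is "bonded with ceramic orthodontic brackets pre-coated with a" flash-free adhesive. The comparator is "a conventional adhesive resin (Clarity Advanced Brackets APC II, 3M Unitek) on the other side". Both sides use the Clarity Advanced line and differ in the adhesive pre-coat.
- **Randomisation.** "The side allocation and order of bonding will be randomized for each patient". The order of debonding is randomised too.
- **Staff.** Ten calibrated clinicians and their assistants carry out the procedures. The text does not say who bonds, debonds, scores or cleans up for a given patient, or where the allocation is recorded.
- **Expectation.** Background presents shorter chair time as the promise of flash-free adhesives. Item 4 of Anticipated outcomes repeats it as a possibility for cleanup.

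Masking is not mentioned anywhere, for any person or outcome.

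**The concern.** A stopwatch is objective, but it measures the interval up to a decision. Here the decision is a visual one about gloss. An operator who knows which side carries the new product, and expects it to clean up faster, can stop a little sooner there or polish a little longer on the other side without intending to. ARI is also a judgement, though a more constrained one.

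Amount of remaining adhesive and cleanup time are two of the four comparisons listed under Purpose. Randomising the side balances anatomy and handedness, and randomising debonding order balances fatigue and sequence. Neither keeps the product's identity from the person judging, so neither removes a systematic difference in how the two sides are judged.

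The debonding visit also differs from the bonding visit. At bonding, excess adhesive is scaled away in the conventional group only, so the clinician cannot be masked. Debonding comes after treatment is complete, the side varies at random between patients, and the bracket line is the same on both sides. Some concealment is therefore plausible at that visit, and the plan does not ask for any.

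**Working it through.** The document gives no standard deviation, effect size or power calculation, so there is no stated figure to reproduce. The check has two parts.

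**1. Does anything in the text close the gap?**

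| Feature in the plan | What it controls | Does it conceal the product? |
|---|---|---|
| Randomised side | Anatomy, handedness | No |
| Randomised debonding order | Sequence, fatigue | No |
| Calibrated clinicians | Differences between operators | No |
| Published index at fixed magnification | Freedom in ARI scoring | No |
| Visual verification of removal | Incomplete cleanup | No; the verifier may be the operator |

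Each feature narrows the room for judgement. None addresses knowledge of the allocation.

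**2. What could a shift do to cleanup time? (illustration only)**

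Inputs from the document: 30 patients (Methods) and a significance level of 0.05 (Statistical analysis).

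Assumptions: two-sided testing, no true difference, a paired t-test, and a systematic shift of *b* standard deviations of the within-patient difference.

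The test has 29 degrees of freedom and critical value 2.045. Its noncentrality is *b* × √30 = *b* × 5.477. The rejection probability is the chance that a noncentral t variable falls outside ±2.045.

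| Assumed shift *b* | Noncentrality | Rejection rate |
|---|---|---|
| 0 | 0 | 5% |
| 0.1 | 0.548 | 8.3% |
| 0.2 | 1.095 | 18.5% |
| 0.3 | 1.643 | 35.5% |

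Statistical analysis names Student's t-test or the Mann-Whitney U test and does not mention a paired form. I therefore simulated an unpaired t-test (58 degrees of freedom, critical value 2.002) on the same 30 pairs, with equal variances and the same shifts. The within-patient correlation is a further assumption.

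| Assumed correlation | *b* = 0 | *b* = 0.1 | *b* = 0.2 | *b* = 0.3 |
|---|---|---|---|---|
| 0 | 5% | 8% | 19% | 37% |
| 0.3 | 2% | 4% | 10% | 24% |
| 0.5 | 0.7% | 1.5% | 5% | 13% |

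In every row the rejection rate rises with the shift. The level depends on the test form and the correlation, and the document fixes neither. With an unpaired test and correlation 0.5, even a shift of 0.2 SD only brings the rate to about the nominal 5%. None of these figures applies to ARI, which is to be analysed with a Cochran-Armitage test.

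**The case against.** The strongest objection is that concealment may achieve little. ARI is scored and cleanup is done after the brackets are off, so the operator is looking at the adhesive, which is what differs between sides. If the two remnants can be told apart on enamel, hiding the allocation list masks little. If the clinician who bonded the patient also debonds, that person saw excess adhesive removed on one side only. This stands: the document does not say whether the remnants look different or who debonds. It limits how much masking can be promised, but it is not a reason to leave the allocation in view.

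The existing safeguards also deserve credit, particularly for ARI, which is less open-ended than a gloss criterion.

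Four stronger readings are tempting, and the document does not support them:

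- *The assessors are unmasked.* The text is silent. It supports only that no masking is specified.
- *Full masking is available without extra staff.* Withholding a record and coding a sheet need no added person. Whether a different clinician can debond depends on scheduling that the plan does not describe.
- *Both outcomes are biased towards the new product.* A possible decrease is anticipated for cleanup time. For ARI no expected or favourable direction is stated.
- *The false-positive rate is 36%.* That figure needs an assumed shift of 0.3 SD and a paired test that the plan does not name.

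The plan's description of itself as an independent assessment is not a promise of blinding either, and the point does not rest on it.

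**Conclusion.** The point holds in a limited form. As written, the plan leaves a judged stopping rule and a judged score without any specified protection from knowledge of the allocation, and it anticipates a possible benefit on one of those two outcomes. The exposure is clearest for cleanup time. For ARI the risk is smaller and its direction is unstated.

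The size of any bias is unknown and cannot be obtained from the document. The rejection rates above show only that a modest systematic shift could matter with 30 patients. They rest on an assumed shift, an assumed test form and, in the unpaired case, an assumed correlation, so they should not be cited as the trial's error rate. What justifies acting is the low cost of the remedy, even if it masks only in part.

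**What to change.** Add to Adhesive remnant cleanup:

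1. The side-allocation record is kept out of the debonding chart until ARI and both cleanup times are recorded.
2. ARI sheets carry only the patient code and tooth number.
3. Where existing scheduling allows, one of the ten clinicians who did not bond the patient does the debonding, scoring and cleanup.
4. The operator records, for each patient, whether the allocation was known or guessed.

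The cost is a short protocol addition and a change to the chart form. Items 1, 2 and 4 need no added staff, and item 3 is conditional on scheduling.

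The downside is that masking may be only partial. The operator may remember the side, learn it when a failed bracket is rebonded, or recognise the remnant. Item 4 shows how often the allocation was known or guessed. If masking proves incomplete, the report should state this as a limitation of the cleanup-time and ARI comparisons.

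### An under-specified Kolmogorov-Smirnov pre-test chooses between two unpaired tests for the time outcomes; one fixed paired analysis should replace it

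*Combined protocol and SAP*

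**What the plan says.** The Statistical analysis section of the combined protocol and SAP states that "the data will be tested for normality (Kolmogorov-Smirnov test"). Group differences then go to a Student's t-test "if the data are normally distributed and a Mann-Whitney U test if the data are non-normally distributed". For every test, P-"values of less than 0.05 will be considered statistically significant", so the pre-test also runs at 0.05.

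The design is split-mouth. Under Methods, the sample is "Thirty consecutive patients presenting for comprehensive orthodontic treatment with fixed appliances", each patient receives both adhesives, and "The side allocation and order of bonding will be randomized for each patient".

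Two outcomes are stopwatch times. Under Bonding time: "The time taken to bond each side will be timed to the nearest second using a digital stopwatch". Under Adhesive remnant cleanup: "The time taken to clean up the residual adhesive in each quadrant will be timed to the nearest second using a digital stopwatch". Each gives 30 times per adhesive.

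The section does not state whether K-S is Lilliefors-corrected. It does not state whether the test is applied to each group, to pooled data or to within-patient differences, or what happens if the two groups disagree. It names no paired test and no transformation. No SD, skewness, effect size or power is given.

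**The concern.** Bonding and cleanup times carry the chair-time aim; Anticipated outcomes looks for a result "together with a possible decrease in chair time when using a “flash-free” product". The plan lets the trial's own data choose the test for both, through a step whose behaviour depends on details left open.

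The standard K-S critical value assumes that mean and SD are known in advance. When they are estimated from the same 30 values, that critical value is far too lenient and the test seldom rejects. The Lilliefors version corrects this. Two competent analysts following the plan could therefore use different tests on the same data and might reach different verdicts.

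Both tests, as named, also compare independent groups, although every patient supplies a matched pair of times. At stake are power and reproducibility, not false positives.

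**Working it through.** The plan gives no power or sample-size figure, so there is none to reproduce. From the documents: n = 30 patients, both adhesives in each, alpha 0.05. Assumed: two-sided tests, log-normal times, a gate that opens to the rank test if either group rejects, and the spreads and effects shown below.

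**1. How often the gate detects skew.** At n = 30 the 5% critical value is D > 0.2417 for uncorrected K-S and D > 0.1589 with the Lilliefors correction. Simulated rejection rates (20,000 runs), uncorrected / Lilliefors:

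| Log SD (skewness) | One group | Either group | Pooled, n = 60 |
|---|---|---|---|
| 0.2 (0.61) | 0.1% / 12.5% | 0.3% / 23.1% | 0.4% / 20.6% |
| 0.3 (0.95) | 0.5% / 21.7% | 0.9% / 38.8% | 1.8% / 40.0% |
| 0.4 (1.32) | 1.4% / 35.0% | 2.8% / 57.7% | 6.2% / 61.7% |
| 0.5 (1.75) | 3.9% / 48.4% | 7.5% / 73.4% | 16.7% / 79.1% |
| 0.8 (3.69) | 23.0% / 82.4% | 40.2% / 96.8% | 67.1% / 98.8% |

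At log SD 0.5 the gate opens in anything from 3.9% to 79.1% of trials, depending only on choices the plan leaves open.

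**2. Cost of the gate with the unpaired tests as named.** The log effect was set to (1.96 + 0.84) × s × √(2/30), with s the log SD. This gives an unpaired log-scale t-test about 80% power. Power at within-patient correlation 0 (6,000 runs):

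| Log SD | Raw t | Mann-Whitney | Uncorrected gate | Log t | Log t minus gate |
|---|---|---|---|---|---|
| 0.3 | 75.9% | 75.3% | 76.0% | 77.7% | 1.7 |
| 0.5 | 73.8% | 75.6% | 74.8% | 78.8% | 4.0 |
| 0.6 | 70.9% | 75.1% | 73.1% | 78.0% | 4.9 |
| 0.8 | 66.3% | 75.6% | 74.2% | 78.2% | 4.0 |
| 1.0 | 60.0% | 76.2% | 75.5% | 78.9% | 3.4 |

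The largest gap at correlation 0.5 was 5.7 points. Where the raw t-test suffers most, the uncorrected gate opens often enough to recover most of the loss.

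**3. Cost of the gate once the tests are paired.** Assumed time ratio 0.85. Ranges cover repeated simulation runs.

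| Log SD between / within patients | Uncorrected gate | Lilliefors gate | Signed-rank | Log-ratio t |
|---|---|---|---|---|
| 0.5 / 0.25, clean | 58–60% | 61% | 62–64% | 67–71% |
| 0.5 / 0.20, 5% of sides 2.5 times slower | 47–49% | 62% | 63–64% | 58–59% |
| 0.3 / 0.20, 3% of sides slow | 57% | – | 72% | 68% |

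- Clean case: a gate that always chose the rank test would gain about 3 to 4 points. The rest of the gap to the log ratio comes from the log scale, which neither branch of the plan contains.
- 5% slow sides: 59 − 47 = 12 points against the log ratio and 64 − 47 = 17 against signed-rank. Lilliefors critical values remove nearly all of this.
- In that scenario the two K-S versions chose different tests in 63% of data sets and gave opposite significance verdicts in 16%. The two groups disagreed on normality in 20% (uncorrected) or 37% (Lilliefors).
- With log SDs 0.2 / 0.2 the gate costs about 2 points.

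**4. Cost of ignoring pairing.** In the setting of step 2 at correlation 0.5, the uncorrected gate has about 81 to 86% power and a paired log-scale t-test about 97%, a gain of 11 to 16 points. About 10 to 11 of these come from pairing: at log SD 0.3, for example, unpaired log t has 86.8% and paired 96.7%.

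A hand check with log SDs 0.25 / 0.20 and ratio 0.85:

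- Log effect = ln(1/0.85) = 0.1625.
- True SD of the mean log difference = 0.20 × √(2/30) = 0.0516.
- Paired t: 0.1625 / 0.0516 = 3.15, which on 29 df gives 86% power.
- Unpaired t uses a total SD of √(0.25² + 0.20²) = 0.320 and a standard error of 0.320 × √(2/30) = 0.0827. It needs a difference above 2.00 × 0.0827 = 0.1655. Power ≈ Φ((0.1625 − 0.1655)/0.0516) = Φ(−0.06) = 48%.

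Simulation agrees: about 47% unpaired and 84 to 86% paired.

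**5. Size.** The paired procedures, gated or fixed, held 3.5 to 5.6%. The unpaired tests at correlation 0.5 ran at about 0.5 to 0.9% (gated, up to 1.3%), which is conservative.

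**The case against.** A reader might infer that the gate almost never detects skew and therefore costs about ten points of power. The documents do not support that. They name neither the K-S version nor the skewness, and with Lilliefors critical values detection is far from negligible. In the clean paired case most of the ten-point gap belongs to the log scale. In the slow-side case the Lilliefors-gated test, at 62%, does slightly better than the log-ratio t-test.

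A reader might also infer that the gate examines each group's times rather than the differences. The plan refers only to the data; the defect is that it does not say.

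The spreads that hurt the gate may be too wide for bonding time. Clinicians are calibrated and five teeth are summed per side. The 20-second cure per bracket adds a fixed 5 × 20 = 100 seconds, if curing falls inside the timed interval. With log SDs of 0.2 to 0.3 between and 0.2 to 0.25 within patients, the gated loss was about 2 to 5 points against the log ratio and 1 point or less against signed-rank.

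Student's t-test could in principle be run paired. The plan does not say so, and its alternative, Mann-Whitney, is an independent-samples test.

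Finally, the log ratio changes the estimate from seconds to a percentage, which is partly a preference. All these points stand, and they limit the size of the problem. They do not defend a data-chosen test with unstated details.

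**Conclusion.** The point holds in a limited form. The normality gate is under-specified, and the choice of test can turn on software defaults and on which data are tested. Its own power cost is small for clean skewed times, about 1 to 6 points. It reaches about 12 to 17 points only if K-S is uncorrected and occasional sides run very slow. No inflation of the false-positive rate is shown. The larger weakness in the same sentence is the lack of pairing: about 10 to 11 points at an assumed correlation of 0.5, and more at higher correlation, as in the hand check (0.25² / 0.320² = 0.61).

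Skewness, slow-side rate, effect size and within-patient correlation are all assumptions, because the documents give none. Clustering by clinician was not modelled. The case for change rests on the unstated choices, the missing pairing and the low cost of the remedy.

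**What to change.** Delete the normality pre-test and the rule that depends on it. Pre-specify one paired analysis for each time outcome, for example:

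> Bonding time and cleanup time will each be analysed by a paired t-test on the within-patient log ratio (flash-free to conventional), reported as a time ratio with 95% CI. The Wilcoxon signed-rank test on within-patient differences will be a fixed sensitivity analysis, and the mean within-patient difference in seconds with 95% CI will be reported alongside.

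If the investigators prefer seconds as the primary scale, a paired analysis of the differences, fixed in advance, would also remove the gate and restore the pairing; it would forgo the modest gain from the log scale. Means and SDs in seconds remain as description.

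The cost is two sentences in the Statistical analysis section, with no new data and no change in sample size. The small downside is that a log-scale estimate is a percentage change, so seconds saved must be reported beside it.
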